6.8.1.1 Adverse Events of Special Notification

Table 1 Adverse Events of Special Notification

Adverse Events of Special Notification:
AEs related to the IMP administration procedure
Suspected or confirmed cases of opportunistic or serious infections that in the investigator's opinion might be related to the IMP
Unexpected reactions (e.g., hypersensitivity, immunological, toxic or other as consequence of a change in the construction or function of the viral vector [e.g., generation of replication competent virus])
AEs related to product failure (including lack of efficacy)
AEs related to mandatory concomitant medication (e.g., immunosuppression)
AEs related to medical devices which form part of the product or are used for application of the product
Development of any new/recurrent cancer.

The categories of adverse events qualifying for special notification are shown above. Please see Section 7.2 of the protocol for more detail.

6.8.1.2 Severity of Adverse Event

If an AE changes severity over time, the maximum severity (i.e. intensity) will be reported.

6.8.1.3 Relationship between IMP and Adverse Event

Please refer to [section 7.3.2](#) of the protocol for the definition of Related and Not Related to IMP.

6.8.2 Changes in Abdominal Ultrasound

To monitor subjects for liver fibrosis and potential occurrences of liver malignancies, abdominal ultrasound assessments will be performed. These ultrasound assessments will occur every 6 months beginning with the Month 30 Post-Treatment Visit.

A table will be used to summarize normal and abnormal results at each visit. All abdominal ultrasound data will be listed.

6.8.3 Physical Examination (Including Height and Weight)

Any physical examination abnormality identified at the Screening will be documented in the subject's source documents and on the medical history eCRF. Any physical examination abnormality reported after the Screening Visit for a subject is to be reported as an adverse event. Thus, these will be included in listings of adverse events and summarized in adverse event summaries, if applicable. Abnormalities seen at the Screening examinations will be recorded as Medical History and listed.

6.8.4 Hematology and Serum Chemistry

The following serum chemistry safety laboratory parameters are taken at each visit: Serum electrolytes (sodium, potassium), creatinine, gamma-glutamyltransferase (GGT), aspartate aminotransferase (AST), alanine transaminase (ALT), alkaline phosphatase (ALP), C-reactive protein (CRP), albumin, total bilirubin, and glucose (non-fasting).

The following hematology safety laboratory parameters are taken at each visit: Hemoglobin, hematocrit, platelet count, red blood cells, and white blood cells with differential count (all expressed in % as well as in absolute numbers), activated partial thromboplastin time (aPTT) and prothrombin time (or INR [International Normalized Ratio]).

If there are multiple laboratory values for the same parameter at pre-dose of a visit or within the same post-dose study time window (if applicable) at a visit, the last value will be chosen for analysis.

Summary statistics (n, mean, median, standard deviation, minimum, and maximum) for the baseline assessment and for the pre-dose value and change from baseline at each post-baseline visit for scheduled lab assessments of continuous laboratory variables will be tabulated.

Table 2 Lab Parameters

Hematology	
Hemoglobin	White blood cells
Hematocrit	aPTT
Platelet count	Prothrombin time
Red blood cells	
Serum Chemistry	
Sodium serum electrolytes	ALP
Potassium serum electrolytes	C-Reactive Protein
Creatinine	Albumin
gamma-glutamyltransferase	Total Bilirubin
AST	Glucose (non-fasting)
ALT	
Coagulation	
aPTT	
PT	
Serology	
HIV 1/2 antibody differentiation	Antibodies detected/ not detected
HIV 1/2 screen	Reactive/Non-reactive
HBsAG	HBV DNA
	HCV RNA
Local Laboratory	
AST	
ALT	

A Clinically Significant Laboratory Abnormality as identified by the investigator after the study drug is administered will be recorded as an Adverse Event and tabulated as an AE in the AE analysis. Abnormalities occurring prior to the drug administration will be noted in medical history and presented in a data listing.

All laboratory data will be stored in the database with the units in which they were originally reported. Laboratory data not reported in International System of Units (SI units; Système International d'Unités) will be converted to SI units before data analysis.

The baseline measurement for a laboratory parameter will be the last available measurement prior to the study drug administration.

Table 3 Protocol-Recommended Study Time Window for Clinical Lab Assessments

Protocol-Recommended Study Time Window	Protocol-Recommended Time Interval for the Study Time Window
Post IMP 1 hour	±15 minutes
Post IMP 2 hours	±15 minutes
Post IMP 3 hours	±15 minutes
Day 1	±15 minutes
Day 3	±1 day
Week 1 to Week 12	±2 days
Week 14 to Week 26	±3 days
Week 31 to Week 48	±5 days
Week 52	±5 days
Month 18 to Month 90	±14 days

Summary statistics (n, mean, median, standard deviation, minimum, and maximum) for the baseline assessment and change from baseline at each post-baseline visit for scheduled lab assessments of continuous laboratory variables will be tabulated. Data from unscheduled visits will not be used for the by-visit summaries (unless they were assigned to a scheduled visit based on the use of an analysis window as given in [Section 6.3](#) under the subsection “[Time Windows for Statistical Analysis](#)”). Data from both scheduled and unscheduled visits will be listed. Both scheduled-visit data and unscheduled-visit data are candidates for clinically significant values. Percentages of subjects in each maximum post-baseline grade for a treatment will be calculated for each pre-dose grade for the treatment and also for all baseline grades combined. Laboratory abnormal values on-treatment will be flagged as High or Low values based on laboratory reference ranges provided by the laboratory that provides the respective laboratory data. The reference ranges for the central laboratory (Medpace) are provided in Appendix 4. These flags along with the reference ranges will be provided in the laboratory data listings.

Potentially Clinically Significant Laboratory Values Above/Below a Clinically Relevant Threshold on-treatment, based on CTCAE 4.03 and other criteria, will be identified based on the following thresholds:

Table 4 Potentially Clinically Significant (PCS) Laboratory Parameter Criteria

Central Laboratory	Post Baseline Criteria
Serum Chemistry	
Sodium serum electrolytes	NA
Potassium serum electrolytes	<3.0 mmol/L >6.0 mmol/L
Creatinine	>2 x ULN
Gamma-glutamyltransferase	NA
AST	>2 x Baseline
ALT	>2 x Baseline
ALP	>2 x ULN
CRP	NA
Albumin	NA
Total bilirubin	>2 x ULN
Glucose (non-fasting)	NA
Hematology	
Hemoglobin	<8.0 g/dL (<80 g/L) Increase of >40 g/L to a value above the ULN (upper limit of normal)
Hematocrit	NA
Platelet count	<50 x 10 ⁹ /L >999 x 10 ⁹ /L
Red blood cells	NA
White blood cells with differential count	<2 x 10 ⁹ /L >35 x 10 ⁹ /L
CD4+ count	≤200/μL
Coagulation	
aPTT	NA
PT (or INR (International Normalized Ratio))	NA
Serology	
HBsAg	NA
HBeAG	NA
HBV DNA	NA
HCV RNA	NA
Local Laboratory	
AST	>3 x ULN
ALT	>3 x ULN

NA: Not Applicable

Clinically significant laboratory values will be tabulated. All laboratory data for the parameter identified as potentially clinically significant for a subject will be listed. Low platelet counts are counted as being clinically significant only if they occur \geq 4 weeks after IMP administration.

The data from the parameters AST and ALT concentrations (ratio to ULN) will also be presented in plots of individual profiles. Note that AST and ALT elevations will be examined in the framework of clinically significant laboratory values as described above.

On the listings, the reference range and flag indicating if the measurement in question is outside the reference range will be provided.

6.8.5 Vital Signs

Changes from Baseline in post-dose systolic blood pressure, diastolic blood pressure, pulse, and body temperature will be tabulated, where baseline is defined as the last assessment prior to IMP administration.

A **Clinically Significant Abnormality** in vital signs identified by the investigator will be recorded as an Adverse Event if it occurs after dose is administered. These adverse events will be included in the AE summaries; abnormalities prior to the start of treatment will be noted in medical history and listed.

Potentially clinically significant changes in systolic and diastolic blood pressure will be defined based on the following criteria:

Table 5 Potentially Clinically Significant Criteria for Systolic and Diastolic Blood Pressure Parameters

Parameter (mmHg)	Post-Baseline Criteria
Systolic Blood Pressure, increase	≥ 180 and increase from baseline ≥ 20
Systolic Blood Pressure, decrease	≤ 90 and decrease from baseline ≥ 20
Diastolic Blood Pressure, increase	≥ 105 and increase from baseline ≥ 15
Diastolic Blood Pressure, decrease	≤ 50 and decrease from baseline ≥ 15

mmHg = millimeter of mercury.

Vital sign measurements (Heart rate, systolic blood pressure, diastolic blood pressure, pulse, body temperature, weight, height) during the study will be displayed in a vital signs listing.

A summary of baseline weight, height, and BMI will be presented by treatment.

Summary statistics (n, mean, median, standard deviation and range) of the absolute value and change from baseline for systolic blood pressure, diastolic blood pressure, pulse, and body temperature will be tabulated by visit, and time point. Data from unscheduled visits will not be used for the by-visit summaries (unless they were assigned to a scheduled visit based on the use

of an analysis window as given in Table 6 below). Data from both scheduled and unscheduled visits will be listed. Time windows will be derived for each post-baseline visit using the time intervals for the study time windows detailed in Table 6.

Table 6 Analysis Study Time Windows for Vital Signs Assessments

Calculated Study Time Window (hours)	Time Interval for the Study Time Window
0.5	>0 to <45 min. post-dose
1	≥45 min. to <1.5 hr. post-dose
2	≥1.5 hr. to <2.5 hr. post-dose
3	≥2.5 hr. to <3.5 hr. post-dose
4	≥3.5 hr. to <5.0 hr. post-dose
6	≥5.0 hr. to <7.0 hr. post-dose
8	≥7.0 hr. to <10.0 hr. post-dose
12	≥10.0 hr. to <18 hr. post-dose
24	≥18 hr. to <30 hr. post-dose

6.8.6 Anti-FIX Antibodies

Blood sampling for measurement of anti-FIX antibodies will take place at the time points as specified in Table 2 and Table 4 of the Protocol. All data will be listed.

6.8.7 FIX Inhibitors

Blood sampling for measurement of FIX inhibitors will take place at the time points as specified in Table 2 and Table 4 of the Protocol.

The investigator may instigate that blood samples for FIX inhibitors are taken at additional visits in case (of suspicion) of detection of inhibitors as judged by the investigator.

All data will be listed.

6.8.8 FIX Recovery

Factor IX recovery will be assessed by measurement of Factor IX activity (%) 30 minutes after infusion of a challenge dose of FIX. This is referred to as Factor IX Recovery “maximum concentration [C_{max}] (%)”. Incremental recovery will be measured as the increase in activity (%) per unit infused (% per U/kg): C_{max} (%) minus Factor IX Activity (%) pre-Factor IX challenge, divided by the Factor IX Challenge dose (which is 40 U/kg). FIX recovery will be performed at baseline (Day 0 pre IMP). Additionally, measurement of FIX recovery and incremental recovery should be done at suspicion of FIX inhibitor as judged by the investigator.

All data will be listed.

6.8.9 Total (IgG and IgM) and Neutralizing Antibodies to AAV5

Blood sampling for measurement of Total (IgG and IgM) and Neutralizing Antibodies to AAV5 will take place at the time points as specified in [Table 2](#) and [Table 4](#) of the Protocol.

All data will be listed.

6.8.10 AAV5 capsid-specific T cells

Sampling for AAV5 capsid-specific T cells will take place at the time points as specified in [Table 2](#) and [Table 4](#) of the Protocol. In case of ALT elevation > 2x baseline, an additional sample should be taken.

All data will be listed and data will also be presented in plots of patient individual profiles.

6.8.11 Inflammatory Markers

Blood samples will be taken to assess IL-1 β , IL-2, IL-6, IFN γ and MCP-1 (monocyte chemotactic protein-1) using enzyme-linked immunosorbent assay (ELISA). In case of ALT elevation > 2x baseline, an additional sample should be taken.

All data will be listed.

6.8.12 Vector DNA in Semen and Blood

Sampling of Vector DNA in Semen and Blood will take place at the time points specified in [tables 2](#) and [4](#) of the Protocol.

Sampling should continue for the individual patient and for a specific matrix until 3 consecutive negative samples have been detected for the patient for that particular type of matrix.

All data will be listed. Furthermore, each individual patient profile will be presented graphically per matrix.

Time to first vector negative will be defined for each type of matrix and each patient as the post-treatment time point where a negative result is measured for the first time in a consecutive order of 3 or more time points with a negative result. Negative result is defined as a result of either '0' or '< LOD' (limit of detection). The time to first vector negative will be flagged on the above-mentioned listings and will also be summarized.

6.9 Statistical Analyses for the Month 60 CSR Addendum

The same analyses that are to be done for the Week 52 main CSR (and the 2.5 year CSR) – as described in [Sections 6.3, 6.4, 6.5, 6.6, 6.7, and 6.8](#) – will be repeated for the Month 60 CSR, but using the entire 60 months (instead of 52 Weeks [or 2.5 years]) of data.

7. CHANGES FROM METHODS PLANNED IN THE PROTOCOL

Beginning with the 2.5-year (data cut) analysis, the contamination rule (for factor IX activity analysis) is hereby refined as follows. Factor IX activity assessments post-AMT-061 that are within 5 half-lives of exogenous factor IX use are considered contaminated and will be excluded from the analysis. Going forward, this 5-half-life contamination rule replaces the 10-day contamination rule. The rationale is to improve accuracy. By contrast, the protocol currently states the following: “The required wash out period (in order to consider a factor IX activity level to be “unaffected” – i.e., “uncontaminated”) will be 10 days.”.

8. STATISTICAL SOFTWARE

Data processing, statistical screening, descriptive reporting and analysis of the efficacy and safety data will be performed using SAS (Version 9.4 or higher).

APPENDIX 1: DATA HANDLING RULES

Programming of the tables, listings and figures will be performed using SAS Version 9.4 or a more recent version. The following table presents the algorithms to be used in SAS to calculate the derived variables, including rules for handling other missing data or partial dates, or irregular/unexpected data issues.

Category	Description	Data Handling Rule
1. Age (years)	Age (years)	Age = integer part of ([Informed Consent date – Birth date + 1]/365.25)
2. Medical History	Medical History Begin Date of Condition	Begin date of condition will be imputed for all subjects as the 1 st of the month for the purpose of computing the onset day.
3. Surgical History	Surgical History Date of Surgery	Date of surgery will be imputed for all subjects as the 1 st of the month for the purpose of computing the onset day.
4. First Treatment Date	date/time of first study treatment	The date and time (24 hr. clock) of the first dose of IMP study treatment will be taken from the Dosing eCRF.
5. Last Visit Date	Date of Last Visit	Date of last visit according to the Visit eCRF.
6. Last Study Participation Date (STDM variable, typically named RFPENDTC)	Last Study Participation Date (STDM variable, RFPENDTC), where SDTM denotes Study Data Tabulation Model	Last study participation date is defined as last known date of contact, which is the later of the following dates: last visit date, date of the last dose, date of last contact if lost-to-follow-up, date of telephone follow-up, or death date.
7. Study Day Definitions	Study Day for assessment/event which occurs on or after the start of study treatment	Study Day = Date of assessment/event – date of the first dose of study treatment + 1.
	Study Day for assessments/events on days prior to the first dose of study treatment in the study	Study Day = date of assessment/event – first dose date of treatment in the study.
	Dose Day	Dose Day in the study is defined as the study day of the first dose of study treatment in the study (Study Day 1).
	Last Study Day	For subjects who did not receive study treatment in the study, Last Study Day is

Category	Description	Data Handling Rule
		
defined as (the later of the last visit date and the date of last contact for subjects lost-to-follow-up from the Study Completion/Early Discontinuation CRF) – Date of Screening Visit + 1.
 
For subjects who received study treatment in the study, Last Study Day is defined as (the later of the last visit date and the date of last contact for subjects lost-to-follow-up from the Study Completion/Early Discontinuation CRF) – first dose date in the study + 1.

8. Duration of event	The duration of any event	The duration of any event is defined as (stop date – start date + 1).
9. Multiple assessments for the same visit	Vital Sign and Laboratory assessments	
 All data will be listed in data listings. The last of multiple valid assessments within a post-baseline study time window will be used for summaries. If there are multiple laboratory values for the same parameter at post-baseline pre-dose of a visit, the last value will be chosen for analysis. The average of all available pre-dose vital sign measurements for a vital sign parameter taken prior to the start of dosing for the Treatment Period will be used for calculation of baseline for a parameter.
10. Special Lab Value Handling for Safety Lab values	Lab values with a prefix such as '>', '<', '+' and 'Less than' etc....	
 '>': use the available original value +0.001 in the analyses. '<': use the available original value -0.001 in the analyses. '+': use the available original value without the prefix in the analyses. '>=': use the available original value in the analyses. '<=': use the available original value in the analyses.
11. Prior and concomitant medication / treatment	Prior and concomitant medication/treatment	1. A medication/treatment (including herbal treatments, vitamins, non-pharmacological treatment such as psychotherapy as appropriate) will be considered prior if the

Category	Description	Data Handling Rule
		
start date of the medication/therapy is before the date of AMT-061 dosing.
 
2. A medication/therapy will be identified as a concomitant (i.e. “post-treatment concomitant”) medication/therapy if it is being continued by the subject at the date of AMT-061 dosing or is any new medication/therapy received during the post-treatment period. A medication with end date that is the same as the AMT-061 dosing date will not be considered to be concomitant (i.e. “post-treatment concomitant”). However, a medication with both start date and end date on the date of AMT-061 dosing is considered to be "post-treatment concomitant".
 
3. Any medication/therapy that cannot be identified as Prior or Concomitant will be considered as being in each of the possible categories depending on available information.

12. Adverse event	Missing severity	For the AE summary by severity, an AE with missing severity will be deemed as Severe.
	Missing relationship to study drug	For AE summary by relationship, an AE with a missing relationship to study drug will be deemed as Definitely related.
	Treatment-emergent adverse event	
An adverse event is considered treatment-emergent if an event occurs (or if there was a worsening [intensity and/or severity changed to worsened grades]) on or after the administration of the IMP. An adverse event that begins on the same date as the administration of the IMP is treatment-emergent if the AE begins after the time of administration or if the time of AE onset is unknown.
 
A death is considered to be treatment-emergent if any of the adverse events that led to the death are treatment emergent.
 
If the AE start date is partial/missing, then

Category	Description	Data Handling Rule
		
 • If AE start date is completely missing, then the AE is considered as treatment-emergent. • If both AE start month and day are missing and AE start year is the same or after the first dose year, then the AE is considered as treatment-emergent. • If AE start day is missing and AE start year and month are the same or after the first dose year and month, then the AE is considered as treatment-emergent. 
Missing/incomplete (partial) AE start and end dates will not be imputed for data listings.

13. Hard coding	Hard coding for data analysis	Hard Coding is not allowed during data analysis unless agreed to in writing by uniQure.
14. CCI	CCI	CCI

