- 2. Positive factor IX inhibitor test at screening
- 3. Screening laboratory values:
 - a. ALT >2 times ULN
 - b. AST >2 times ULN
 - c. Total bilirubin >2 times ULN
 - d. Alkaline phosphatase (ALP) >2 times ULN
 - e. Creatinine >2 times ULN
- 4. Positive human immunodeficiency virus (HIV) serological test at screening, not controlled with anti-viral therapy as shown by CD4+ counts ≤200/µL or by a viral load of >200 copies/mL
- 5. Active infection with hepatitis B or C virus as reflected by hepatitis B surface antigen (HBsAg), hepatitis B extracellular antigen (HBeAg), hepatitis B virus deoxyribonucleic acid (HBV DNA) or hepatitis C virus ribonucleic acid (HCV RNA) positivity, respectively, at screening
- 6. History of hepatitis B or C exposure, currently controlled by antiviral therapy

- 7. Known coagulation disorder other than hemophilia B
- 8. Thrombocytopenia, defined as a platelet count below 50×10^9 /L, at screening
- 9. Known severe infection or any other significant concurrent, uncontrolled medical condition including, but not limited to, renal, hepatic, cardiovascular, hematological, gastrointestinal, endocrine, pulmonary, neurological, cerebral or psychiatric disease, alcoholism, drug dependency or any other psychological disorder evaluated by the Investigator to interfere with adherence to the protocol procedures or with the degree of tolerance to the IMP
- 10. Known significant medical condition that may significantly impact the intended transduction of the vector and/or expression and activity of the protein, such as disseminated intravascular coagulation, accelerated fibrinolysis, and profound liver fibrosis
- 11. Known history of an allergic reaction or anaphylaxis to factor IX products
- 12. Known uncontrolled allergic conditions or allergy/hypersensitivity to any component of the IMP excipients
- 13. Known medical condition that would require chronic administration of steroids
- 14. Previous gene therapy treatment
- 15. Receipt of an experimental agent within 60 days prior to screening
- 16. Current participation or anticipated participation within one year after IMP administration in this trial in any other interventional clinical trial involving drugs or devices

Maximum Duration of Subject Involvement in the Trial:

- Planned duration of screening period: maximal six weeks
- Planned duration of treatment: 1 day (single dose)
- Planned duration of follow-up: 52 weeks, plus long-term safety follow-up until Month 60

Endpoints:

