6.8 Safety Analyses

6.8.1 Adverse Events

The version of the Medical Dictionary for Regulatory Activities (MedDRA) that is current at the time of database lock will be used to code verbatim terms for AEs for final analysis of the data. A glossary of MedDRA preferred terms used for adverse events reported in the study along with the associated Investigator's verbatim term will be provided.

An adverse event is considered on-treatment (i.e. treatment-emergent) if an event occurs after the dose of study drug, or if the AE worsened during the study after the dose of IMP (intensity and/or severity changed to a worsened grade). An adverse event that begins on the same date as the dose of study drug is treatment-emergent if the AE begins after the time of dose or if the time of AE onset is unknown. Adverse events are collected from the time informed consent is signed.

All treatment-emergent AEs are tabulated by SOC and preferred terms within each SOC according to the MedDRA terminology list. TEAEs will also be tabulated by severity (mild/moderate/severe using the Common Terminology Criterion for Adverse Events severity grades) and by relationship (related/not related) to trial medication, using frequency counts (number of subjects with event and number of events) and percentages. Similar tables will be created for TEAEs leading to premature treatment discontinuation (i.e. for which the infusion of study drug was stopped mid-infusion), deaths, and SAEs.

These summary tables will be presented by decreasing frequency of occurrence based on SOC and Preferred Term.

An AE overview table will be created displaying the number of subjects (and percentage) experiencing an event and the number of events for: Any TEAE, Mild/moderate/Severe TEAE, Related/Unrelated TEAE, Serious TEAE, and TEAEs leading to discontinuation (i.e. for which the infusion of study drug was stopped mid-infusion).

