The summary tables will be accompanied by individual subject listings of all AEs, including information on AE number, actual AE description, date/time of start and end of AE, preferred term (MedDRA), SOC (MedDRA), severity, relationship/causality, type of AE, seriousness and outcome. Pre-existing AEs will be flagged. Pre-existing AEs are not considered to be treatment-emergent, except in case of worsening during/after trial treatment (to be collected as separate AE). Separate listings will be created for SAEs and deaths. AEs qualifying for special notification will also be tabulated for those types that can be identified programmatically. The categories of AEs qualifying for special notification are tabulated below.

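### SAP Appendix 1 item 12 classes adverse events with an incomplete start date as treatment-emergent without looking at the end date, so an event that ended before dosing can be counted as treatment-emergent

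*SAP*

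**What the plan says.** SAP Appendix 1 sets out the algorithms to be programmed, including those for partial dates. Item 12 defines an AE as treatment-emergent if it occurs or worsens on or after administration of the study product. It then gives three rules for incomplete start dates. Each one makes the event treatment-emergent:

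- Nothing known: "If AE start date is completely missing, then the AE is considered as treatment-emergent".
- Year only: "If both AE start month and day are missing and AE start year is the same or after the first dose year".
- Year and month only: "If AE start day is missing and AE start year and month are the same or after the first dose year and month".

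None of the three uses the end date. Item 12 mentions end dates once, and only for display: "Missing/incomplete (partial) AE start and end dates will not be imputed for data listings".

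The end date is nevertheless available. SAP 6.8.1 lists "date/time of start and end of AE" for every AE. The same section says "Adverse events are collected from the time informed consent is signed", and the protocol synopsis gives "Planned duration of screening period: maximal six weeks", which may be prolonged in consultation with the sponsor. On events that predate treatment, SAP 6.8.1 says "Pre-existing AEs are not considered to be treatment-emergent, except in case of worsening during/after trial treatment", and protocol 9.10 says the same.

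**The concern.** The three rules are meant for events whose timing relative to dosing is unknown. They also capture events whose timing is known. If an AE has a recorded end before the infusion, it cannot have begun or worsened afterwards, whatever is missing from its start date. Item 12 still classes it as treatment-emergent, against its own definition and against the rule on pre-existing events.

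At stake is the content of the tables of treatment-emergent AEs, which are produced for the Week 6 interim report and under SAP 6.8 and 6.9 for the later reports. In a trial of three subjects, one wrongly classed event is visible in any percentage it enters.

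**Working it through.** The plan gives no figure to reproduce here, so the check applies the rules as written to constructed cases.

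**1. One hypothetical event.** It starts on 2 August and ends on 6 August; dosing is on 15 August of the same year. The end date is fully recorded.

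| Start date as recorded | Item 12 as written | With an end-date check |
|---|---|---|
| Complete | not treatment-emergent | not treatment-emergent |
| Day missing | treatment-emergent | not treatment-emergent |
| Day and month missing | treatment-emergent | not treatment-emergent |
| Completely missing | treatment-emergent | not treatment-emergent |

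The event is the same in every row. Only the completeness of its start date changes the result under the written rule.

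**2. How often the rule misclassifies, given an incomplete start date and a known end before dosing.** Assume that onset is 2 to 42 days before dosing (41 values, matching a six-week screening period), that dosing is equally likely on each of 365 days, and that all combinations have equal weight. That gives 365 × 41 = 14,965 combinations.

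- *Completely missing:* always treatment-emergent, so 100%.
- *Year only:* wrong whenever onset falls in the dosing year. For an onset k days before dosing, this holds for 365 − k dosing dates. The mean of k over 2 to 42 is 22, so the share is (365 − 22)/365 = 343/365 = 94.0%.
- *Year and month only:* wrong whenever onset falls in the dosing month. For dosing on day d of the month (d ≥ 2), d − 2 of the onsets qualify. A month of L days gives (L − 1)(L − 2)/2 combinations: 435 for 31 days, 406 for 30 and 351 for 28. Over the year, 7 × 435 + 4 × 406 + 351 = 5,020, and 5,020/14,965 = 33.5%.

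With an end-date check all three shares become 0%. They are conditional on the record being incomplete in this way and are not expected error rates. The documents do not say how many such records exist.

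**3. Effect on a table.** SAP 5.1 gives N = 3, so one subject is 1/3 = 33.3 percentage points. The DMC charter allows for six subjects; the step would then be 1/6 = 16.7 points. The full step applies to a preferred term only if that subject has no other treatment-emergent event with the same term, and to the row for any treatment-emergent AE only if he has no other such event at all.

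**4. Route into the related-event table.** The event must have been assessed as related or possibly related, or its relationship must be missing, in which case SAP 6.3 and item 12 treat it as related.

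**The case against.** The best defence is that the main text already answers the point. SAP 6.8.1 and protocol 9.10 exclude pre-existing events that do not worsen, item 12 opens with the right definition, and the three rules are only a fallback for unknown onset. A sensible programmer would read them that way. This stands as evidence of intent. It does not remove the conflict: the sentence on pre-existing events gives no rule for incomplete dates, while Appendix 1 does and is what will be programmed. Item 13 also bars hard coding without written agreement, so such a record could not simply be overridden. Item 11, just above, already uses the end date relative to dosing to classify medications.

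It can also be said that the rule is deliberately conservative, like the SAP's defaults for missing severity, missing relationship and incompletely described bleeds. Its error is indeed toward over-counting and hides no harm. But a worst-case default is meant for doubt, and here the end date removes the doubt.

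Four further points stand and limit the size. The trigger needs an incomplete start date together with a usable end date before dosing. Monitoring against source and data queries should complete some dates. Protocol 7.1 sends illnesses identified during screening procedures to medical history. Every AE is listed individually with its dates, so a reader of three subjects' listings could spot the case.

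A reader might infer that screening events tied to usual factor IX treatment or to procedures will fill the treatment-emergent tables. The documents do not support that: no section links screening AEs to factor IX use, and protocol 7.1 says a medical or surgical procedure is not itself an AE.

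**Conclusion.** The point holds as a minor one. As written, item 12 gives a wrong classification for an AE with an incomplete start date and a recorded end before dosing, in conflict with its own definition and with SAP 6.8.1 and protocol 9.10. The largest effect of one such event is 33.3 percentage points on one preferred term in three subjects, under the conditions in the working. The number of affected records is not documented and is probably small or zero.

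It would be wrong to infer that the safety profile is materially distorted or that the dose decision is affected. The analysis is descriptive, no such record is shown, and DMC charter section 9 ties dose confirmation to factor IX activity of at least 5% alongside a safety review. The effect on the DMC's own summaries cannot be fully checked, because their table shells are in a separate document.

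**What to change.** Add to each of the three rules in item 12: *unless the AE end date, complete or partial, shows that the event ended before IMP administration.*

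A partial end date is decisive when its known part precedes dosing, for example an end month before the dosing month. Events whose end date is missing, too partial to decide, or on the dosing day with unknown time stay treatment-emergent, so real uncertainty is still handled conservatively. The clause should not hide a worsening after dosing, because SAP 6.8.1 has worsening collected as a separate AE and protocol 7.4 has recurrences reported separately.

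The cost is one clause in the SAP and one condition in the program, using data already collected. Only AEs that ended before dosing can be affected, so a single look at the three subjects' pre-dose records would show whether any reported table changes.
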